8.0 ASSESSMENT OF SAFETY

8.1 Definitions

8.1.1 Adverse Event

An **Adverse Event (AE)** is defined as any new event that may jeopardize the patient which the study investigator physician perceives may be directly related to the enrolment in the pilot study or to the assigned arm. Adverse events are not study related if they are related primarily to the underlying disease. All AEs are to be documented and assessed for relatedness. If related to the study intervention and occurring from baseline up to 24 hours (by the final visit), the AE will be recorded on the eCRF and coded as per the most recent edition of the Common Terminology Criteria for Adverse Events (CTCAE).

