8.1.2 Expected adverse events with Ready-Heat® blankets

Prolonged direct skin contact with the Ready-Heat blanket has been known to cause mild burns. The manufacturer specifies the need for careful supervision when used with “the elderly....people with sensitive skin and those who can't feel heat or regulate heat”¹³. Given that some of the enrolled patients may be sedated due to clinical condition, the study products will be applied with the express direction to avoid direct skin contact. The recommendation will be made to use a standard blanket as an intermediary between the skin and the study product.

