8.1.5 Serious Adverse Event (SAE)

A serious adverse event (SAE) in the study is defined as:

- a) any event that is fatal or immediately life threatening, permanently disabling, severely incapacitating, or requires prolonged inpatient hospitalization, or
- b) any event that may jeopardize the patient and requires medical or surgical intervention to prevent one of the outcomes listed above, AND
- c) which the attending physician perceives may be directly related to enrolment in the study, or to the assigned arm.

SAEs will be considered to be study-related if the event follows a reasonable temporal sequence from the study intervention and could readily have been produced by the intervention. Adverse events are not study related if they are related primarily to the underlying disease.

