9.0 Early Termination and Reasons for Withdrawal

While it is not anticipated to cause discomfort, patients may find that they are not able to continue with the study product due to the ongoing heat. Patients are permitted to withdraw consent at any time if they desire and will not undergo further trial investigations if they do so. Participants withdrawing from the study should be contacted by the study research team requesting a final visit and to follow up with any unresolved adverse events. Once withdrawn from the study, no further study procedures or evaluations should be performed, or additional study data collected. However, every effort should be made to obtain permission to document the reason for withdrawal and to collect participant outcomes, such as survival data up to the protocol-described end of participant follow up period, where possible. Any data collected prior to the withdrawal of consent may be retained and used by the sponsor. If the patient withdraws from the study, the research team will notify the patient's most responsible physician.

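### Read literally, the adverse event definition in 8.1.1 excludes mild burns and heat intolerance, which conflicts with 8.1.2 and 8.2.4 and could leave burns counted but ungraded and without causality review

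*Combined protocol and SAP*

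**What the plan says.** Section 8.1.1 defines an adverse event as "any new event that may jeopardize the patient", with the further condition "which the study investigator physician perceives may be directly related to the enrolment in the pilot study or to the assigned arm". It then sets two steps that follow from that status. The first is "All AEs are to be documented and assessed for relatedness". The second applies to events related to the intervention and occurring by 24 hours: "the AE will be recorded on the eCRF and coded as per the most recent edition of the Common Terminology Criteria for Adverse Events".

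Section 8.1.2 is headed "Expected adverse events with Ready-Heat® blankets" and states: "Prolonged direct skin contact with the Ready-Heat blanket has been known to cause mild burns".

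Limb (b) of the serious adverse event definition in 8.1.5 covers "any event that may jeopardize the patient and requires medical or surgical intervention to prevent one of the outcomes listed above".

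Section 8.2.4 separates severity from seriousness, accepts that an event may matter little medically, and has investigators grade adverse events by CTCAE. Section 8.2.5 lists what need not be recorded: pre-existing conditions, likely manifestations of the underlying disease or events common in this population, and elective procedures.

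Skin redness and burns are also a safety outcome (synopsis; outcome 16 in section 3.6). They are collected as one item at Visit 3 (5.4.1.3) and summarized descriptively in total and by arm (7.2).

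Heat intolerance is foreseen only in section 9.0: "patients may find that they are not able to continue with the study product due to the ongoing heat".

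**The concern.** The entry condition for any adverse event borrows a phrase that 8.1.5 uses for serious ones. In a massively bleeding patient, a mild burn or discomfort from heat would not ordinarily be thought to endanger the patient. An investigator who applies 8.1.1 as written could therefore decide that neither is an adverse event, although 8.1.2 says that mild burns are.

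Mild burns are the one harm that 8.1.2 names for this device. Section 8.1.2 also notes that some patients may be sedated and repeats the manufacturer's caution about people who cannot feel heat. The pilot is meant to inform the design of a definitive trial. If burns go ungraded and without causality review, that trial starts with a count of skin events but no account of how severe they were or whether the blanket caused them. Two safety displays in the same report could also disagree, with burns in the skin summary and none in the adverse event listing.

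**Working it through.** No arithmetic applies. The check sets the passages side by side and follows two events through them.

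**What depends on the label of adverse event**

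| Step | Section | Applies to |
|---|---|---|
| Documentation and relatedness assessment | 8.1.1 | adverse events |
| eCRF entry and CTCAE coding | 8.1.1 | related adverse events up to 24 hours |
| Unexpectedness | 8.1.3 | adverse events |
| Causality | 8.2.1 | adverse events |
| Severity by CTCAE | 8.2.4 | adverse events |
| Source record, form and CTCAE category | 8.2.5 | adverse events |

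An event that is not called an adverse event has no stated route to any of these steps.

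**A mild burn under the blanket**

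1. Under 8.1.1 read literally, it does not endanger the patient, so it is not an adverse event.
2. Under 8.1.2, it is an expected adverse event. Section 8.1.3 relies on that list when it defines an unexpected event.
3. Under 8.2.4, minor events belong on the severity scale.
4. Under 8.2.5, low severity is not among the reasons for leaving an event unrecorded.
5. No section says which of these prevails.
6. Whatever the answer, the burn enters outcome 16 and the Visit 3 skin item. That item is a frequency that pools redness with burns. Visits 1 and 2 add whether the blanket lay directly on the skin. The listed items include no grade or relatedness for the skin event.

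On the literal reading, the burn is counted but neither graded nor assessed for causality.

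**A patient who cannot tolerate the heat**

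1. Under 8.1.1 read literally, this is not an adverse event.
2. It is absent from 8.1.2, from the safety outcomes in 3.6 and from the safety measurements listed in 7.2.
3. It can be recorded as a reason for removal (5.1, 5.3.3.5, Visit 2 item 3, and outcome 8 in section 3.3) or, with permission, as a reason for withdrawal (9.0). None of these routes calls for a grade or a relatedness assessment.

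**Comparison with 8.1.5.** Limb (b) also requires medical or surgical intervention to prevent a listed serious outcome. The two definitions share a phrase, but the serious threshold is higher.

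**The case against.** The strongest reply is that the protocol read as a whole treats a blanket burn as an adverse event. Section 8.1.2 says so in its heading, 8.1.3 builds on it, and the exclusions in 8.2.5 do not mention mild events. The jeopardy phrase is undefined and left to the investigator's judgement. This stands as far as it goes. A reader might infer that mild burns definitely fall outside the definition, and the documents do not settle that. What they show is one rule in conflict with others and nothing to say which governs.

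A reader might also infer that burns could go unreported, or that the trial could present a clean safety record while burns occurred. The documents do not support this. Redness and burns are counted and summarized by arm whatever the adverse event definition says, and in a randomized comparison those counts themselves bear on causality. For the same reason, an upper confidence limit attached to zero adverse events in the 37 intervention patients would not measure the loss: the burns would be visible in the skin count, and any burn rate used would be an assumption.

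Nor is the threshold for any adverse event the same as that for a serious one, given the extra requirement in 8.1.5(b). And heat intolerance is not lost altogether, because removal reasons are collected and an adverse reaction is one of the examples given.

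A grade and relatedness field on the skin item would be a lighter remedy. It would close the gap for burns, but would leave the contradiction in the text and do nothing for heat intolerance.

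**Conclusion.** The concern holds in a limited form. Section 8.1.1 conflicts with 8.1.2 and with the grading scheme in 8.2.4. If investigators follow 8.1.1 literally, burns would be counted by arm but could lack a CTCAE grade and a causality review, the adverse event listing could disagree with the skin count, and heat intolerance would be kept only as a removal or withdrawal reason.

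The conclusion rests on two assumptions: that some investigators would apply 8.1.1 as worded, and that the case report form carries no grade or causality field for skin events beyond the items listed in 5.4.1. The size cannot be put in numbers, since the documents give no rate of burns or of heat intolerance. The loss is in the detail of the safety data, not in the count of burns. It is worth correcting because it touches the device's one named harm and the correction is short.

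Separately, 8.1.1 makes perceived relatedness a condition of being an adverse event and then asks that all adverse events be assessed for relatedness, which is circular. The point made here, about severity, does not depend on that.

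**What to change.** Reconcile 8.1.1 with 8.1.2:

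- Remove the jeopardy condition from 8.1.1 and keep it in 8.1.5.
- State that any skin redness or burn at the site of a warming blanket, in either arm, and any heat intolerance that leads to blanket removal, is recorded as an adverse event whatever its severity, with CTCAE grade and relatedness. For these events relatedness should be a field to complete, not a condition of entry.
- State in 8.2.5 that the exclusion for likely manifestations of the underlying disease does not apply to skin events at blanket sites.

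The rest of that exclusion can stay, which limits the volume of forms. Widening the definition to every unfavourable event in either arm is not needed to cure this defect. It would be a larger redesign of adverse event collection in a population with many injury-related events.

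The change affects recording only and leaves the management of patients as it is. The cost is the wording in 8.1.1 and 8.2.5 and some extra adverse event forms over a 24-hour window in 74 patients. Their number cannot be stated because no event rate is given.

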8.1.2 Expected adverse events with Ready-Heat® blankets

Prolonged direct skin contact with the Ready-Heat blanket has been known to cause mild burns. The manufacturer specifies the need for careful supervision when used with “the elderly....people with sensitive skin and those who can't feel heat or regulate heat”¹³. Given that some of the enrolled patients may be sedated due to clinical condition, the study products will be applied with the express direction to avoid direct skin contact. The recommendation will be made to use a standard blanket as an intermediary between the skin and the study product.

8.1.3 Unexpected Adverse Event

An unexpected adverse event is defined as any adverse event that is not identified in section 8.1.2 or in nature, severity or frequency in the current Health Canada Product Monograph.

8.1.5 Serious Adverse Event (SAE)

A serious adverse event (SAE) in the study is defined as:

- a) any event that is fatal or immediately life threatening, permanently disabling, severely incapacitating, or requires prolonged inpatient hospitalization, or
- b) any event that may jeopardize the patient and requires medical or surgical intervention to prevent one of the outcomes listed above, AND
- c) which the attending physician perceives may be directly related to enrolment in the study, or to the assigned arm.

SAEs will be considered to be study-related if the event follows a reasonable temporal sequence from the study intervention and could readily have been produced by the intervention. Adverse events are not study related if they are related primarily to the underlying disease.

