7.2 Final Analysis Plan

Demographic and clinical characteristics will be summarized in total and by two arms using mean, SD, median (interquartiles) and range for continuous variables, and percentages for categorical variables. Wilcoxon rank-sum test, Chi-square test or Fisher exact test will be applied for comparing continuous or categorical variables between two arms, as appropriate. To investigate the primary objective on the feasibility of using the Ready-Heat® chemical heating blanket, the proportion (and 95% CIs) of patients with an increased body temperature by at least 1°C at 8 hours from arrival to the trauma bay will be calculated and compared between two arms using Chi-square or Fisher exact test as appropriate. Line graph (with mean and SD) of body temperature over the first 8 hours of blanket application will be plotted for two treatment arms. To search for significant time trends in two arms on the hourly body

temperature measurements within first 8 hours of blanket application, linear mixed effects repeated model will be performed with both fixed (time in hours, treatment arms, and arms by time interaction) and random (patient) effects. To compare treatment effects on the coagulation parameters (platelet count, INR, fibrinogen level), perfusion parameters (pH, base deficit, serum lactate), and hemoglobin levels measured on arrival and over the first 8 hours, linear mixed effects repeated model will also be performed with both fixed and random effects. Skewness and Kurtosis will be tested on the distribution of coagulation, perfusion and hemoglobin parameters. Natural logarithm transformation will be applied to normalize the distribution if necessary. Descriptive analysis will be summarized in total and by arms for safety measurements (i.e., number of units of blood products transfused, number of times blanket is placed directly on patient skin, and number of times patients developed redness and/or skin burns). All analyses will be conducted using Statistical Analysis Software (SAS version 9.4, Cary, NC) and R package (version 4.3.0). P-value < 0.05 will be considered statistically significant.

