8.2.5 Adverse Event Recording

Investigations into potential adverse events should be done during each contact with a participant.

Investigations may be done through specific questioning and, as appropriate, by examination.

Information on all adverse events should be recorded promptly in the source document, and assessed by an investigator in a timely manner allowing sufficient time to meet required reporting timelines for SAEs and serious unexpected adverse drug reactions (SUADRs) if needed. Adverse event CRFs should be completed using source documents by a delegated research team member in a timely manner/within 15 days of site awareness. All clearly related signs, symptoms, and abnormal diagnostic procedures should be recorded in the source document, though should be grouped under one diagnosis. Each diagnosed

adverse event should then be categorized in accordance with the revised NCI Common Terminology Criteria for Adverse Events (CTCAE).

The following are not considered AEs and therefore do not require recording:

- Pre-existing diseases or conditions identified and recorded at screening/baseline unless, at the discretion of the investigator, the disease or condition worsens in severity or frequency
- At the discretion of the investigator, events considered likely manifestations of the underlying disease or that commonly occur in the study population independent of study drug exposure
- Elective medical or surgical procedures.

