8.3.5 Reporting and Entry Timelines

Study investigators will report SAEs to the sponsor within the following timelines:

- All deaths and immediately life-threatening events, whether related or unrelated, will be recorded and reported to the sponsor within 24 hours of site awareness.
- Serious adverse events other than death and immediately life-threatening events, regardless of relationship, will be reported to the sponsor within 72 hours of site awareness.

Adverse event information will be entered into the CRF in a timely manner and **no later than 15 days** from the time the investigator becomes aware of the event.

Serious adverse event information will be entered into the CRF in a timely manner/**within 72 hours** from the time the investigator becomes aware of the event.

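### Perceived relatedness is built into the AE and SAE definitions and the Section 8.1.1 eCRF rule, which contradicts Sections 8.2.5 and 8.3.5 and would make any by-arm AE/SAE table from the eCRF non-comparable

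*Combined protocol and SAP*

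**What the plan says.** - **SAE definition (Section 8.1.5).** Limb (a) covers death, immediate threat to life, lasting disability, severe incapacity and a longer hospital stay. Limb (b) covers events needing treatment to avert one of those. Clause (c), joined by AND, adds that the event is one "which the attending physician perceives may be directly related to enrolment in the study, or to the assigned arm".
- **AE definition (Section 8.1.1).** An AE is an event "which the study investigator physician perceives may be directly related to the enrolment in the pilot study or to the assigned arm". The section continues: "All AEs are to be documented and assessed for relatedness". It then limits eCRF entry: "If related to the study intervention and occurring from baseline up to 24 hours".
- **AE recording (Section 8.2.5).** "Information on all adverse events should be recorded promptly in the source document", with AE CRFs to follow within 15 days. The investigator may leave out events put down to the underlying disease or common in this population.
- **Reporting (Section 8.3.5).** "All deaths and immediately life-threatening events, whether related or unrelated, will be recorded and reported to the sponsor within 24 hours" of site awareness. Other SAEs go to the sponsor within 72 hours, whatever their relationship to the study. CRF entry is due within 15 days for AEs and 72 hours for SAEs, with no relatedness condition.
- **Causality (Section 8.2.1).** The investigator judges whether the investigational product caused or contributed to the event. An unsure judgement counts as related to the study product.
- **Analysis (Section 7.2).** "Descriptive analysis will be summarized in total and by arms for safety measurements". A list in parentheses follows: transfused units, direct placement on skin, and redness or burns.

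**The concern.** Whether an event happened and whether the treatment caused it are separate questions. The usual order is to record the event first and judge its cause afterwards. Here the judgement of cause decides whether the event counts at all (Sections 8.1.1 and 8.1.5) and whether it reaches the trial database (Section 8.1.1), while other sections assume that unrelated events are recorded and reported. Site staff cannot tell which rule governs.

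Two things are at stake. An SAE judged unrelated may not be reported although Section 8.3.5 asks for it. And an eCRF that holds only events related to the study intervention gives an uneven count across arms in an open-label trial. The pilot is meant to inform a definitive trial, so the definitions may be carried forward.

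**Working it through.** The plan states no AE rate or event count, so there is no figure to reproduce. The check is a comparison of the texts, followed by an illustration on assumed inputs.

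**1. SAE definition against Section 8.3.5.** The structure a, or b, AND c can be read in two ways.

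- *(a or b) and c.* Every SAE is perceived as possibly related. If that perception is the same judgement as relationship in Section 8.3.5, no unrelated SAE exists and the 72-hour rule's wording has nothing to act on.
- *a or (b and c).* Limb (a) events are SAEs without a relatedness test, and Section 8.3.5 works for them. A limb (b) event judged unrelated is still not an SAE, so the conflict remains there.

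The conflict therefore holds at least for limb (b), and arguably for limb (a). The last part of Section 8.1.5, which says when an SAE counts as study-related, also presupposes SAEs that are not.

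**2. AE definition and eCRF entry.** Section 8.1.1 requires perceived relatedness for an event to be an AE, then asks for AEs to be assessed for relatedness, then filters eCRF entry on the result. Sections 8.2.5 and 8.3.5 require CRF entry for AEs without that filter. An AE judged unrelated is kept off the eCRF by Section 8.1.1 and entered under the other two.

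**3. Who assesses relatedness, and against what.** Relatedness is assessed by the attending physician in Section 8.1.5 and by the investigator in Sections 8.1.1 and 8.2.1. Sections 5.1 and 5.3.1 say that only the statistician stays blinded (Sections 2.2 and 5.1 also mention blinded outcome assessors, but give them no role in causality). The reference in Section 8.2.1 is the investigational product. Section 6.1 uses the term study intervention for the Ready-Heat blanket, which control patients do not receive. Under the Section 8.1.1 filter, a control-arm AE would thus tend to stay off the eCRF.

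**4. Illustration.** Let n = 37 per arm (Section 7.1), p = true event proportion, equal in both arms (assumed), and q = probability that an intervention-arm event is judged related (assumed 0.10 to 0.50). Take q = 0 in control, which is the strict reading of the Section 8.1.1 phrase. Expected eCRF events = n × p × q. Events left off, both arms together = 2 × n × p − n × p × q.

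| p | True events per arm (37 × p) | eCRF, intervention | eCRF, control | Left off, both arms |
|---|---|---|---|---|
| 0.10 | 3.7 | 0.37 to 1.85 | 0 | 5.55 to 7.03 |
| 0.30 | 11.1 | 1.11 to 5.55 | 0 | 16.65 to 21.09 |
| 0.50 | 18.5 | 1.85 to 9.25 | 0 | 27.75 to 35.15 |

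For p = 0.30 and q = 0.50: 37 × 0.30 × 0.50 = 5.55 on the eCRF, and 22.2 − 5.55 = 16.65 left off. With equal true rates, the filter alone produces an arm difference and undercounts both arms. This shows direction only, since p and q are assumptions and the control zero is built in.

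**The case against.** The strongest case on the other side is that the wording conflict does little harm. A reader might infer four stronger conclusions, and the documents support none of them.

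- *That the planned by-arm safety summary is biased.* Section 7.2 lists what it will summarise, and AE and SAE records are not on the list. No by-arm AE analysis is specified.
- *That control-arm burns are excluded by rule.* Redness and burns are a named outcome in Section 3.6. Skin safety events are collected at Visit 3 (Section 5.4.1.3) with no stated relatedness or arm restriction.
- *That events judged unrelated are never captured.* Section 8.2.5 puts AEs in the source document, Section 8.3.5 covers deaths and life-threatening events, and Section 8.2.1 treats unsure cases as related.
- *That control-arm AEs are zero by definition.* Both definitions admit events related to enrolment or to the assigned arm, so a control event can qualify. The zero follows only from the narrower eCRF phrase in Section 8.1.1, which other sections contradict.

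Clause (c) may also be a drafting slip. Or the attending physician's perception may be a first screen and the investigator's assessment a second step. On that reading Section 8.3.5 keeps some content, but only for events that pass an unblinded screen. Finally, a relatedness filter can be defended for a Class I device used for 8 hours. Without clause (c), much of the course of a life-threatening injury could qualify as an SAE.

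All of this stands as a limit on the consequence, and the last point requires the fix to be bounded. It does not remove the contradiction, and the unsure-means-related rule softens the filter only for the study product.

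**Conclusion.** The point holds as an internal contradiction with a limited consequence. Sections 8.1.1 and 8.1.5 cannot be applied together with Sections 8.2.5 and 8.3.5. In Section 8.1.5 the conflict is certain for limb (b), subject to the two-step reading, and arguable for limb (a). Followed as written, the definitions drop SAEs judged unrelated that Section 8.3.5 says must be reported, and the eCRF phrase tends to exclude control-arm AEs. A by-arm AE or SAE table drawn from the eCRF would not be comparable.

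The Section 7.2 measures are outside the problem. So are deaths and life-threatening events, provided that Section 8.3.5 is followed. The size for other events is unknown. The conclusion assumes that study intervention in Section 8.1.1 means the Ready-Heat blanket and that those judging causality know the arm. The correction is worth making because it is cheap and improves safety capture, but no planned analysis depends on it.

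**What to change.** 1. Remove clause (c) from Section 8.1.5 and the relatedness condition from the AE definition in Section 8.1.1.
2. Record relatedness as a separate attribute under Section 8.2.1, with one named assessor role.
3. Replace the Section 8.1.1 eCRF filter with one rule for both arms: enter all deaths, life-threatening events, other SAEs, and skin or overheating events up to 24 hours, regardless of relatedness. Make the CRF-entry sentences in Sections 8.2.5 and 8.3.5 refer to this rule.
4. To bound the work, apply the existing Section 8.2.5 exemption for likely effects of the underlying injury identically in both arms, but never to deaths, life-threatening events, or skin or overheating events. State in Section 8.3.5 how exempted events are treated, so that the two sections agree.

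In the same edit, reconcile the 24-hour form for all SAEs in Section 8.3.2 with the 72 hours in Section 8.3.5, and correct the references in Sections 8.2.2 and 8.2.3, which point to 9.1.2 and 9.1.5 instead of 8.1.2 and 8.1.5.

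The cost is protocol wording and modest extra eCRF entry over 24 hours in 74 patients. Without step 4 the entry burden could be considerable in this population. With it, some unblinded discretion remains over other SAEs.
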